Study protocol - Use of the bioabsorbable Activa IM-Nail™ in pediatric diaphyseal forearm fractures: a cohort study of 30 patients Version 3.5 – May 2021 – Protocol ID: H-21004012

Study protocol

Use of the bioabsorbable Activa IM-Nail[™] in pediatric diaphyseal forearm fractures: a cohort study of 30 patients

[name], [name], [name] and [name]

Herlev and Gentofte University Hospital, Copenhagen, Denmark

The Danish Data Protection Agency ID: P-2020-1197 The Danish National Committee On Health Research Ethics ID: H-21004012

Abstract	3
Introduction	4
Background	4
Epidemiology	4
Treatment options	4
Metal Elastic Stable Intramedullary Nailing (ESIN)	5
Hardware removal	5
Bioabsorbable implants	5
Objectives	6
Primary objective	6
Secondary objectives	6
Hypothesis	6
Methods and materials	6
Study design	6
Selection and withdrawal of participants	7
Surgical technique and post-operative regime	9
Risks, side effects and disadvantages	9
Variables	
Outcomes	11
The Radiographic Union Score	11
Faces Pain Scale – Revised (FPS-R)	11
Visual analogue scale	12
Bias	12
Study size	13
Statistics	13
Discussion	13
	40
Ethics and security	
Ethics	
Identification of the implant	
Hospital records Data security	
Data security	14
Publication	15
Perspective	15
Disclosures and economy	15
Literature	16

Abstract

Background

Pediatric diaphyseal forearm fractures are common and one of the most frequent reasons for orthopedic care. Fractures in need of surgery are often treated with metal Elastic Stable Intramedullary Nails (ESIN). Nail removal after 6-12 months is generally advocated. Surgical hardware removal has few complications; however, it is a substantial burden on the child, the family and healthcare economy. Bioabsorbable Intramedullary Nails (BIN) have been developed for the same indications as metal ESIN. The use of bioabsorbable implants would deem hardware removal unnecessary and relieve the child of further surgery and reduce healthcare costs.

Methods

We aim to recruit all children in the catchment area of Herlev and Gentofte University Hospital (Copenhagen, Denmark) with acute unstable diaphyseal forearm fractures. Participants will be operated with BIN and followed consecutively for 2 years with interim analysis of data after 6 months. We will report radiological healing using the Radiographic Union Score (RUS) 3 months after surgery together with any adverse events during follow-up.

Discussion

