Implants made from oriented poly L-lactide-co-glycolide (PLGA) copolymers are strong enough to support fractured bones. The monomers of PLGA are L-lactic acid and glycolic acid, which are part of the normal metabolic chemistry of human cells. PLGA implants undergo a controlled degradation through hydrolysis forming lactic acid and glycolic acid which are absorbed by the cells and metabolized into carbon dioxide and water. The implant retains strength and size for at least eight weeks and over the course of approximately two years the implant will be completely absorbed [28]. Medical grade PLGA implants manufactured by Bioretec Ltd. ([name]) are sterilized with gamma radiation. Gamma radiation also reduces molecular weight of oriented PLGA implants. The reliability and safety of the Activa IM-Nail[™] has been described in the manufacturer's premarket trials and one RCT [7], the implant is FDA and CE approved for the same purpose as in the present study.

Objectives

Primary objective

The primary objective of this study is to evaluate the amount of radiological healing three months after surgery with the Activa IM-Nail[™] for pediatric diaphyseal forearm fractures.

Secondary objectives

The secondary objectives are to report the functional outcome, calculate refracture rate and any other complications up to two years following surgery and to describe MRI findings two years after insertion of Activa IM-Nail™.

Hypothesis

We hypothesize that radiological healing is established three months after surgery with the Activa IM-Nail™.

Methods and materials

Study design

We use a cohort study design [29] conformed to the STROBE Statement [30]. We aim to recruit all children with diaphyseal forearm fractures (cohort) operated with BIN (exposure) and report radiological healing

(outcome). This study design is relevant in reporting radiological healing and calculating absolute risk of adverse events based on the exposure in our cohort.

Selection and withdrawal of participants

Setting

The study will be performed in the Capital Region of Denmark, Europe. Patients in Herlev and Gentofte University Hospital's catchment area (population 700.000 of which 80.000 are children age 3-15) are eligible for recruitment.

Participants

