This study investigates the treatment of pediatric forearm fractures; therefore, this study cannot be conducted in consenting adults. Forearm fractures occur in all age groups and thus it is not possible to select only older children for inclusion. This study is believed to have great positive implications for the participants and successive patients with the same condition.

Participants eligible for recruitment are patients from 2 years of age until physeal closure with an acute traumatic diaphyseal forearm fracture of the radius, ulna or both. Fractures need to be complete (not unicortical or green stick) and displaced more than 50% of bone width or angulated more than 10° in any plane or irreducible or unstable after reduction.

We exclude patients

- with fractures that are well managed conservatively (undisplaced or minimally displaced)
- with previous ipsilateral forearm fracture
- with fractures unsuited for intramedullary nailing (e.g. multifragmentary, metaphyseal or epiphyseal)
- with fractures with ipsilateral wrist or elbow involvement (e.g. Monteggia or Galeazzi variants)
- unable to participate in follow-up
- with existing bone pathology (e.g. tumor, osteogenesis imperfecta, degenerative disease)
- in whom internal fixation is otherwise contraindicated (e.g. active or potential infection)

Recruitment

Recruitment starts May 25th, 2021 and is estimated to take 12 months. Patients may be seen primarily in our Emergency Department (ED) or referred by local clinics or another hospital. Patients with displaced forearm fractures are reviewed daily by the department's trauma surgeons. Any patients eligible for recruitment are referred to the PI for evaluation. Eligible patients are contacted by the PI and invited to a

scheduled visit as soon as possible. The parents are informed of the possibility of bringing an assessor. Parents, and when applicable the child, are informed face-to-face about the project. Parents are given both oral and written information. Patients are recruited at Herlev and Gentofte University Hospital by the principal investigator (PI).

Informed consent

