Studies have shown a 5% risk of nerve injury [32], however all cases had spontaneous recovery of nerve function.

Extra visits to the outpatient clinic

We follow all patients with six visits to the outpatient clinic. This is three more than with standard treatment and might be viewed as a disadvantage.

Radiation

Three extra radiographs are obtained during outpatient visits. A radiograph of an extremity leads to a radiation dose of less than 0.001 mSv and compares to 3 hours of background radiation. Three extra radiographs is far below the threshold of 0.1 mSv.

MRI

Two years after surgery an MRI is performed. We follow a special MRI-protocol without the need for sedation or anesthesia.

Variables

At recruitment baseline data will be collected:

- Demographic data (age, gender, handedness, height and weight)
- Injury data (date and time, left or right arm, location, activity, mechanism, open or closed fracture, diagnosis code, indication for surgery)
- Historical data (metabolic disease, medication, other systemic illness)

After surgery, operative data is collected (date and time of surgery, operative time, closed or open reduction, any complications).

During follow-up in the outpatient clinic data will be collected on:

- Pain (Faces Pain Scale Revised) or VAS according to child's age
- Use of pain medication
- Wound appearance (visible signs of infection)
- Neurovascular status
- Bilateral elbow and forearm range of motion (ROM) measured in degrees by goniometer
- Forearm radiographs in AP and ML planes (Radiographic Union Score)

2 years following surgery MRI findings (absorption of the nail, activity at fracture site, soft-tissue reactions) will be collected.

Outcomes

The primary objective is quantified using the Radiographic Union Scale (RUS) [33] based on degree of callus formation and visibility of fracture line on AP and ML plain radiographs. We define established healing as a RUS of > 9.

Secondary objectives are described as absolute risk of refracture, time to established healing (weeks), pain (Faces Pain Scale – Revised (FPS-R) or visual analogue scale (VAS)), elbow and forearm range of motion (in degrees), visible signs of infection, neurovascular complications and any reoperation. MRI findings (absorption of the nail, activity at fracture site, soft-tissue reactions) after 2 years are described.

The Radiographic Union Score

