To quantify pain in children age 8 and above we will use a visual analogue scale (VAS) (Figure 2). VAS has been extensively investigated in quantifying pain in older children [40,41]. The child is asked to put a mark on the line corresponding to the child's pain at that moment. A mark to the far left equals no pain and a mark to the far right equals worst possible pain. The line is 10 cm long and the child's mark is measured from left to right in cm with one decimal e.g. 3.4 cm equaling a VAS of 3.4. If the child cannot cooperate to using VAS, FPS-R is used instead.

Figure 2 - Visual analogue scale (VAS) for quantifying pain in children age 8 and above.

Bias

We strive to minimize bias in our study. Displaced forearm fractures do not go unnoticed. A strict protocol for referrals for treatment are in place in Denmark. All eligible patients referred to Herlev and Gentofte University Hospital will be asked to participate in the study. We speculate that by enrolling 30 participants the cohort will be representative of the background population. We speculate that these efforts will limit

selection bias. Efforts described in the follow-up section reduce the risk of loss to follow-up. Overall, we find a low risk of bias in our study for the chosen study design and size.

Study size

The surgical procedure for the Activa IM-Nail[™] resembles that of TEN very much and performing surgeons are all experienced traumatologists. All surgeons will be thoroughly introduced to the procedure, the instruments and the implants, thereby minimizing learning curve phenomenon. We predict that 30 participants will be sufficient in establishing the basis for planning a randomized trial.

Statistics

Data will be analyzed using SPSS (SPSS, Chicago, IL, USA). Descriptive statistics will be used to present the patient-related data, number of dropouts, radiological outcome and number of complications (categorical variables). Age and functional outcome (continuous variables) are expected to be expressed as medians with interquartile ranges. Changes in functional outcome between measurements are expected to be analyzed using Friedman test for related non-parametric data. A p-value of <0.05 is regarded as being significant.

Discussion

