Operative treatment with metal ESIN is the preferred technique for stabilizing pediatric forearm fractures. Removal of the metal nails is generally advocated in many countries including Denmark. By using BIN, a second operation to remove the nails is avoided.

The hypothesis is that satisfactory fracture healing is accomplished 3 months after operation with BIN. The only previous study on BIN used forearm rotation and not fracture healing as primary outcome [7]. The authors describe that all 15 fractures operated with BIN had healed after 2 years.

The cost of one Activa IM-Nail[™] (\$400) is approximately 4 times higher compared with a traditional TEN (\$100). However the cost of implant removal is approximately \$1900 [7,42] and the extra implant costs are readily balanced out.

Ethics and security

Ethics

The implant is CE approved for the same indications as the use in this study. Permission from the Danish Data Protection Agency is obtained before the inclusion is initiated. The trial will be conducted in accordance with the Declaration of Helsinki of 1996 and principles of good clinical practice.

As with any treatment in the Danish healthcare system all patients are insured and covered by The Patient Compensation Association (Patienterstatningen).

To quantify any unknown side effects or complications an interim analysis of data will be performed 6 months after recruitment of the last patient. An absolute refracture rate of more than 25% is not tolerated and will be a criterion for stopping the study.

In comparison with the standard follow up of pediatric forearm fractures there are 3 additional visits to the out-patient clinic with radiographs of the forearm in AP and ML view. Collectively, the effective dosage is 0.003 mSv - far below 0.1 mSv and is considered insignificant.

Identification of the implant

The traceability of the device is identified by device name, catalogue number (REF) and batch number (LOT).

Hospital records

No access to the patient's EHR regarding the study is made before informed consent to participate is given.

In order to plan and conduct visits, admission and operation we ask that consent is given to access the patient's EHR. We ask permission to retrieve patient-related data and to read entries regarding visits, admission and operation. We ask permission to access radiographs and MRIs.

We ask that access the patient's EHR is given until the conclusion of the project.

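### The 25% refracture limit has no time horizon or estimator, and the one planned look comes before any child is expected to have two years of follow-up

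*Combined protocol and SAP*

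**What the plan says.** The protocol's Ethics section (under Ethics and security) plans one look: "an interim analysis of data will be performed 6 months after recruitment of the last patient". The next sentence sets the limit: "An absolute refracture rate of more than 25% is not tolerated and will be a criterion for stopping the study". It does not say over what period the rate is measured, in which children, by what estimator, or with what allowance for uncertainty.

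The Abstract describes the interim differently. Children are "followed consecutively for 2 years with interim analysis of data after 6 months", with no statement of what the 6 months are counted from.

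The other relevant places are these:

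- Secondary objectives: the aim is to "calculate refracture rate and any other complications up to two years following surgery".
- Outcomes: "Secondary objectives are described as absolute risk of refracture", with no time point.
- Recruitment: "Recruitment starts May 25th, 2021 and is estimated to take 12 months".
- Study size: "We predict that 30 participants will be sufficient in establishing the basis for planning a randomized trial". No calculation is given.
- Statistics: complications are presented as descriptive counts. No time-to-event method, and no method for unequal follow-up, is named.
- Withdrawal: a dropout's last examination is carried forward, and a child lost before the first follow-up visit leaves the analysis.
- Variables: the list of data collected at follow-up names neither refracture nor its date.

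**The concern.** An absolute risk has a meaning only over a stated period. At the planned interim the children will have been followed for very different lengths of time. A simple proportion of refractured children estimates neither the 6-month nor the 2-year risk, and it depends on how fast recruitment went as well as on the implant. Carrying the last examination forward pushes the same way, because a child who leaves early without a refracture stays in the denominator as a non-event.

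This is the only numerical safety limit in the protocol. Two analysts with the same data could reach opposite answers on whether it has been exceeded, depending on the period and denominator each chose. A figure below 25% at the interim could also be taken as reassurance about a 2-year risk that has not yet been observed.

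**Working it through.** The protocol gives no derivation for the 25% or for the 30 participants, so there is no planned figure to reproduce. The check asks what the limit does if it is applied as a simple proportion at the planned interim.

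**Inputs from the protocol.** The limit is more than 25%. There are 30 children. Recruitment takes 12 months (an estimate). The look is 6 months after the last recruitment. Refracture is an outcome up to 24 months.

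**Assumptions, not in the protocol.** Recruitment is uniform, there is no dropout, and the true 2-year risk is R = 30%. Several patterns of refracture timing are tried.

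**Follow-up at the interim.** The last child has 6 months and the first has 12 + 6 = 18 months, with a mean of 12. No child has 24.

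**Count that exceeds the limit.** 7/30 = 23.3% does not exceed it; 8/30 = 26.7% does. The denominator matters: with 27 children, 7/27 = 25.9% would exceed it.

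**Expected interim proportion.** This is p, the mean of F(t) over t uniform on 6 to 18 months, where F(t) is the cumulative refracture risk and F(24) = 0.30.

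- Constant hazard: λ = −ln(0.70)/24 = 0.01486 per month. Then p = 1 − (e^(−6λ) − e^(−18λ))/(12λ) = 1 − (0.9147 − 0.7653)/0.1783 = 0.162.
- Half of refractures by 6 months, the rest evenly to 24 months: p = 0.15 + 0.15 × (12 − 6)/18 = 0.20.
- Three quarters by 6 months: p = 0.225 + 0.075 × 6/18 = 0.25.
- All by 6 months: p = 0.30.

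**Probability of reaching 8 or more.** This is P(X ≥ 8) with X binomial(30, p).

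| Timing of refractures (R = 30%) | Expected interim proportion | 8 or more of 30 |
|---|---|---|
| Constant hazard | 16% | 10% |
| Half by 6 months | 20% | 24% |
| Three quarters by 6 months | 25% | 49% |
| All by 6 months | 30% | 72% |
| Complete 2-year data, any timing | 30% | 72% |

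The 16% is not a floor. A Weibull time to refracture with shape 1.5, where the hazard rises with time, gives 12.1% and about 2%. With shape 0.5, where it falls, the results are 22.0% and 33%.

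**Higher true risk.** At R = 35%, constant hazard gives an expected 19.2%, and 8 or more is reached in 21% of trials, against 88% with complete 2-year data. Under constant hazard the 2-year risk must be about 44% before the expected interim proportion is 25%.

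**Dependence on recruitment speed.** With constant hazard and R = 30%, recruitment over 6, 12 or 18 months gives expected proportions of 12%, 16% and 20% for the same implant.

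**Sampling error alone.** With complete 2-year data and a true 30%, the limit is missed in 100% − 72% = 28% of trials. An observed 7/30 has an exact 95% confidence interval of 9.9% to 42.3%.

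**Would a fixed time point at the interim sharpen the check?** Under constant hazard with R = 30%, the 12-month risk is 1 − 0.70^(12/24) = 16.3%, almost the same as the expected simple proportion of 16.2%. The 6-month risk is 1 − 0.70^(6/24) = 8.5%, and 8 or more of 30 on that basis occurs in 0.3% of trials. A fixed time point makes the estimate interpretable but not more sensitive to the 2-year risk.

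**The case against.** The strongest reply is that much of the problem has to be inferred. Several stronger readings are tempting, and the documents do not support them.

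- A reader might infer that the plan prescribes a crude proportion. It does not; no estimator is named. That reading is only the natural one, given counts and carry-forward.
- A reader might infer that the limit applies only at the interim and is dropped afterwards. The limit stands in its own sentence and says nothing on when it applies. What can be said is that no other look is described.
- A reader might infer that the 25% is a 2-year limit. The Ethics section does not say so; the two years come from the secondary objective.
- A reader might infer that passing the interim opens the way to the randomised trial. The protocol calls this study a pilot that evaluates safety before that trial, but ties progression neither to the interim nor to the 25%.

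It is also fair to say that a 2-year analysis is already planned, that dilution vanishes if every refracture occurs within 6 months, and that part of the miss probability is small-sample error that complete follow-up would not remove. All children will have been recruited by the interim, so a missed crossing there leads to no further implantations in this study.

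All of this stands, and it limits the claim. It leaves untouched the missing horizon, denominator and estimator, the two unreconciled descriptions of the interim, and the direction of any error.

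**Conclusion.** The concern holds as a gap in definition with a known direction and an unknown size. Applied as a simple proportion at the planned interim, the 25% limit would be set against a quantity that, in expectation, is at most the 2-year risk. For a true 2-year risk of 30%, that quantity is 16% under constant hazard and 30% if all refractures come within 6 months, with 8 or more of 30 reached in 10% and 72% of trials. These figures assume 12 months of uniform recruitment, no dropout and 30 children analysed. Only the gap between the interim result and the 72% from complete data is due to incomplete follow-up; the remaining 28% is the price of 30 children.

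The documents do not show that an implant with a high 2-year risk will pass, because they do not say when refractures occur. They do leave open that it could, and that the interim figure could be misread.

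**What to change.** - **Ethics section.** The sponsor states the time horizon and the denominator of its own 25%, and reconciles the timing of the interim there with the Abstract.
- **Variables and Withdrawal.** Record the date of each refracture. For this outcome, censor dropouts at their last examination instead of carrying it forward.
- **Statistics, interim.** Report the Kaplan-Meier cumulative refracture risk with 95% confidence intervals at 6 and 12 months. Label these as 6- and 12-month risks, and not as evidence that the 2-year risk is tolerable.
- **Statistics, 2-year analysis.** Report the 2-year cumulative risk with its 95% confidence interval beside the same 25% before describing refracture as tolerable.

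This proposes no new threshold, stopping rule or condition for starting the randomised trial. The cost is a few sentences, one Kaplan-Meier table and one added date field; the visits out to two years are already scheduled. The downside is a more modest interim statement, and the interim estimates will not detect a high 2-year risk any better than the simple proportion does. The gain is that each figure has a defined meaning and the 2-year comparison is made explicitly.
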